**Table 2 Study Schedule of S-1 Arm**

Visit ID/Procedure	Baseline		On-Treatment						End of Treatment/Study		
	Baseline Days		Cycle 1 (Day of Cycle)			Subsequent Cycles (Day of Cycle)			End of Treatment i) for S-1	30-Day Safety Follow-up Visit ii)	Survival Follow-up
	-28 to -1	-7 to 0 iii)	1	8	15	1	15	End of Recovery			
Visit Window	0	0	-1 to 0	± 3	± 3	-1 to 0	± 3	± 3	± 3	-7	
Sign ICF	X										
Inclusion/Exclusion	X		X								
Assign Patient Number	X iv)										
Medical History	X										
Baseline Signs and Symptoms	X	X	X								
Physical Exam v)	X	X	X v)	X	X	X v)			X	X	
Height	X										
Vital Signs/Weight v)	X	X				X v)			X	X	
Performance Status v)	X	X	X			X v)			X	X	
ECG	X								X	X	
Hematology v)	X	X		X	X	X v)	X v)		X	X	
Serum Chemistry v)	X	X		X	X	X v)	X v)		X	X	
Coagulation v)	X	X		X	X	X v)	X v)		X	X	
Urinalysis	X	X							X	X	
Pregnancy test vi)		X									
Concomitant Medications vii)	—————→										
AE/Toxicity Assessment vii)	—————→										
Tumor Assessment viii)	X							X viii)	X viii)		
S-1 Treatment ix)			—————→			—————→					
CCI											
Survival Status xi)	—————→										

Abbreviations: AE = adverse event; BID = twice daily; ECG = electrocardiogram; ICF = informed consent; CCI.

- i) End of Treatment: If the decision to discontinue S-1 is made within 2 weeks after the patient's last treatment visit, an End of Treatment visit is not required unless deemed clinically necessary by the investigator. If the decision to discontinue S-1 (because of disease progression or other reasons) is made more than 2 weeks after the last treatment visit, an End of Treatment visit is required. See Section 10.4.1 of the protocol.
- ii) 30-Day Safety Follow-up Visit: If the patient starts new anticancer therapy within 30 days of the end of treatment, the 30-day Safety Follow-up visit should be performed before the start of new anticancer therapy within the 30-day window. See Section 11.13 of the protocol.
- iii) Baseline Assessment (Day -7 to -1) will be obtained within 7 days before treatment on Day 1 of Cycle 1.
- iv) Patient Number Assignment: A patient number will be assigned once a patient has entered study screening (ie, has signed the ICF).
- v) The physical exam, vital signs determination, weight, performance status, laboratory evaluations (hematology, serum chemistry, and coagulation) will be obtained within 1 day before study drug administration on Day 1 of each cycle starting at Cycle 2. After Cycle 4, the Day 15 laboratory evaluations are not required unless clinically indicated by the investigator. After Cycle 6, the laboratory evaluations can be accepted within 2 days before study drug administration on Day 1 of each cycle, if there are no drug-related AEs greater than Grade 2 observed in the latest cycle.
- vi) Pregnancy Test: Pregnancy test is required at Baseline (within 7 days prior to Day 1 of Cycle 1) and at End of Treatment and 30-day Safety Follow-up visit. More frequent pregnancy assessments may be performed as required by local law.
- vii) Concomitant medications and AE/toxicity assessments will be collected from the time of signing of the ICF through 30 days after administration of the last dose of study medication.
- viii) Tumor assessments/scans will be performed at baseline, at the end of every 6 weeks ( $\pm 7$  days) beginning at Cycle 1 Day 1 throughout all the treatment cycles, and at the time of discontinuation. See Section 11.12 of the protocol, Tumor Assessments/Scans for details. Computerized tomography (CT) scans obtained before signing the ICF may be used as the baseline tumor scan if it is within 28 days of the first study drug administration. If the patient has discontinued treatment for reasons other than radiologic disease progression, a CT scan should be performed within 2 weeks of the End of Treatment visit. Following Cycle 6, CT assessments may be adjusted to every 9 weeks.
- ix) S-1 administration: orally BID on Days 1 through 14 of each cycle.

CCI

- j) Survival Follow-up: Obtain survival status (alive/dead) at scheduled 8-week intervals until death. Survival status should be collected for up to approximately 12 months after the first dose of treatment with S-1 of the last patient enrolled or until the target number of events is reached, whichever occurs first, even if consent for study participation has been withdrawn.

#### **4. DATA AND ANALYTICAL QUALITY ASSURANCE**

The overall quality assurance procedures for the study data, statistical programming and analyses are described in the Everest's Standard Operating Procedures. Detailed data management procedures are documented in the Data Management Plan, Data Validation Check Specifications, and Data Review Plan. Detailed statistical and programming quality control and quality assurance procedures are documented in the Statistical Analysis and Programming QC/QA Plan.

The study endpoints and analytic approaches are both prospectively defined and documented in the protocol and in this SAP. The SAP will be finalized prior to the database lock.

#### **5. ANALYSIS POPULATIONS**

The analysis populations defined in this SAP differ slightly from the populations defined in the protocol in order to adhere to the FDA guidance (ICH E9).

##### **5.1 Intent-to-Treat (ITT) Population**

The ITT population is defined as all patients randomized in the study, regardless of whether they actually received any study treatment (TAS-114 or S-1) or not. All analyses using this population will be based on the treatment assigned by IXRS.

##### **5.2 Tumor Response (TR) Evaluable Population**

The TR evaluable population includes all patients in the ITT population with measurable disease (at least one target lesion) at baseline and with at least one tumor evaluation (Patients who have disease progression or have a cancer related death prior to their 1st tumor evaluation will also be considered evaluable.) All analyses using this population will be based on the treatment assigned by IXRS.

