12.1.3.3. Overall Response Assessment

Assessments will be based on the definitions provided in [Table 13](#) and [Table 14](#).

Table 13: Time Point Response for Patients with Target (+/- Non-Target) Disease

Target Lesions	Non-Target Lesions	New Lesions	Overall Response
CR	CR	No	CR
CR	Non-CR/Non-PD or Not all evaluated	No	PR
PR	Non-PD or Not all evaluated	No	PR
SD	Non-PD or Not all evaluated	No	SD
Not all evaluated	Non-PD	No	Not evaluable
PD	Any	Yes or No	PD
Any	PD	Yes or No	PD
Any	Any	Yes	PD

Abbreviations: CR = complete response; PD = progressive disease; PR = partial response; SD = stable disease

Table 14: Time Point Response for Patients with Only Non-target Disease

Non-Target Lesions	New Lesions	Overall Response
CR	No	CR
Non-CR/Non-PD	No	SD
Not all evaluated	No	Not evaluable
Unequivocal PD	Yes or No	PD
Any	Yes	PD

Abbreviations: CR = complete response; PD = progressive disease; SD = stable disease

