14. STATISTICS

This section outlines the statistical methodology to be used to summarize the study results. An SAP will be prepared as a separate document. The SAP will include a more technical and detailed description of the planned statistical summaries and will be finalized prior to closing of the database.

Study Populations

The study populations include safety and efficacy populations.

Safety and Efficacy Populations

All safety and efficacy analyses will be based on patients who received at least 1 dose of TAS-114/S-1 or S-1 control.

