### 6.2.2.2 Overall Response Rate and Disease Control Rate

Overall response rate (ORR) is defined as the proportion of patients with objective evidence of complete response (CR) or partial response (PR). The evaluation of ORR will be based on central independent review of the images (local CT image assessment and collect CT scans for central independent review).

CCI

At the analysis stage, the best overall response will be assigned for each patient as the best response recorded after initiation of study treatment. If applicable, responses recorded after disease progression or initiation of new anti-cancer treatment will be excluded.

The assessment of disease control rate (DCR) will parallel that of ORR, with DCR defined as the proportion of patients with objective evidence of complete response (CR), partial response (PR), or stable disease (SD).

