## 7.3 Protocol Deviations

A CSR reportable Protocol Deviation is related to inclusion/exclusion criteria, conduct of the trial, patient management or patient assessments that impact the safety of the subjects or jeopardize the quality of the study data.

During the conduct of protocol TAS-114-201 the following categories will be used for CSR reportable Protocol Deviations:

- A subject that did not meet entry criteria
- A subject that developed withdrawal criteria but was not withdrawn
- A subject that received the wrong treatment or incorrect dose
- A subject that received an excluded medication
- Critical ICF, GCP and other Protocol Deviations

A CSR non-reportable Protocol Deviation may be important to address and document as part of site management and oversight, but is not considered reportable in the CSR.

The following categories will be used to capture non-reportable PDs.

- SAE reporting
- Informed consent
- Study procedures
- Investigational product (other than incorrect dose or wrong treatment)

Refer to *Protocol Deviation Plan*, Section 2 for details.

The key protocol violations include, but are not limited to:

- No measurable disease (assessed by investigator or central independent review)
- Did not receive at least 2 prior therapies for advanced or metastatic disease condition, including platinum doublet and pemetrexed, docetaxel, or immunotherapy
- No documentation of histologically diagnosed or cytologically proven advanced or metastatic NSCLC patients, either Stage IIIB/Stage IV disease (according to Version 7 of the International Association for the Study of Lung Cancer Staging Manual in Thoracic Oncology), or recurrent disease following radiation therapy or surgical resection

The number of patients with deviations of one or more criteria and the number of patients with key protocol violations will be listed and tabulated for all patients (including screen failures) and ITT population.

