### 7.5.2.2 Overall Response Rate and Disease Control Rate

The overall response rate and disease control rate analyses will be based on the Tumor Response (TR) evaluable population.

ORR and DCR in the efficacy population will be compared between the 2 treatment groups using Fisher's exact test. The estimates and differences will be presented along with the associated exact 95% CIs for each treatment group.

Best response will be summarized into four RECIST categories: complete response (CR), partial response (PR), stable disease (SD), and progressive disease (PD). The summary will also include a category for unevaluable patients if applicable.

CCI

ORR and DCR will also be presented by geographical region.

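### SAP 7.5.2.2 compares ORR and DCR in a subset that depends partly on events after randomisation, and gives that set two names; make ITT the main set and report TR evaluable beside it (minor)

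*SAP*

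**What the plan says.** SAP 5.2 limits the TR evaluable population to ITT patients "with measurable disease (at least one target lesion) at baseline and with at least one tumor evaluation". It then adds an exception: "Patients who have disease progression or have a cancer related death prior to their 1st tumor evaluation will also be considered evaluable".

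SAP 7.5.2.2 opens with "The overall response rate and disease control rate analyses will be based on the Tumor Response (TR) evaluable population". Its next paragraph says "ORR and DCR in the efficacy population will be compared between the 2 treatment groups", using Fisher's exact test. No definition of an efficacy population appears in the readable part of SAP section 5. Protocol section 14 does define the set for efficacy: "All safety and efficacy analyses will be based on patients who received at least 1 dose of TAS-114/S-1 or S-1 control". Protocol 14.1.2.2.2 uses that set for ORR and DCR.

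PFS (SAP 7.5.1) and OS (SAP 7.5.2.1) are analysed on ITT. SAP section 5 says its populations differ slightly from the protocol's, and gives adherence to ICH E9 as the reason. SAP 7.2 will tabulate the size of each population and the reasons for exclusion.

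Two places show that patients without a target lesion are foreseen. SAP 7.3 lists lack of measurable disease, by investigator or central reading, among the key protocol violations. Protocol 12.1.3.3 supplies Table 14, "Time Point Response for Patients with Only Non-target Disease".

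**The concern.** Whether a patient has a tumor evaluation is known only after randomisation and may depend on treatment. An analysis restricted to such patients no longer compares the groups as randomised. In an open-label trial that adds a second drug to S-1, early stopping for toxicity or withdrawal could differ between arms, so equal exclusion cannot be taken for granted.

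The baseline condition adds a second route out. Protocol 12.1.2 always classifies the primary lesion as non-target. A patient whose only measurable lesion is the primary could therefore be eligible and yet have no target lesion.

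The two names make this more than a choice of denominator. Read with the protocol, TR evaluable patients and treated patients are different sets, so two analysts could run the same Fisher test on different patients. At stake are the level of the reported ORR and DCR and, if exclusions are unequal, the difference between arms. The primary PFS analysis is not touched.

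**Working it through.** **Plan's own figure.** The documents give no sample size, power, assumed rate or test level for ORR or DCR, so there is nothing to reproduce. What follows is illustration.

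**Step 1: who is counted.**

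| Randomised patient | TR evaluable | Protocol treated set | ITT |
|---|---|---|---|
| Target lesion, at least one evaluation | in | in if dosed | in |
| Target lesion, no evaluation, progression or cancer-related death first | in | in if dosed | in |
| No evaluation; other death, withdrawal or toxicity | out | in if dosed | in |
| Never dosed, no evaluation, no progression or cancer-related death | out | out | in |
| No baseline target lesion | out | in if dosed | in |

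The three sets differ in the last three rows.

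**Inputs.** 124 patients at 1:1 (SAP 3.5), so 62 per arm assumed. DCR 50% assumed. ORR 7.1%, the earlier S-1 rate in Protocol 6.3, as an anchor only. Fisher two-sided at 0.05 assumed. The number without an evaluation, u, is not in the documents; 3 to 12 per arm is tried. The 10% lost to tumor follow-up in SAP 3.5 is a different quantity and does not give u.

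**Step 2: scenario A, every unscanned patient a failure, all-randomised DCR 50% in both arms.** TR rate = 0.50 × 62/(62 − u) = 31/(62 − u):
- u = 3: 31/59 = 52.5%
- u = 6: 31/56 = 55.4%
- u = 9: 31/53 = 58.5%
- u = 12: 31/50 = 62.0%

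**Step 3: scenario B, missing scans unrelated to tumor control, scanned patients at 50% in both arms.** The TR rate stays at 50%. Counting unscanned patients as failures gives 0.50 × (62 − u)/62: 47.6%, 45.2%, 42.7% and 40.3% for u = 3, 6, 9 and 12.

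**Step 4: rejection rates with no true difference.** Exact enumeration of two independent binomials, summing the probability of tables with Fisher p ≤ 0.05:

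| Unscanned | A: TR gap | A: TR rejects | B: TR rejects | B: ITT gap | B: ITT rejects |
|---|---|---|---|---|---|
| 6 v 6 | 0 | 2.9% | 2.9% | 0 | 2.9% |
| 6 v 3 | 2.8 points | 4.7% | 4.0% | −2.4 points | 3.8% |
| 9 v 3 | 5.9 points | 7.6% | 3.6% | −4.8 points | 5.7% |
| 12 v 3 | 9.5 points | 13.4% | 3.5% | −7.3 points | 9.1% |

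ITT in scenario A rejects in 3.8%. Swapping the arms only reverses the sign of each gap.

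**Step 5: ORR at 7.1%, scenario A.** At 9 v 3, TR reads 8.3% v 7.5% and rejects in 3.3%. At 12 v 3 it reads 8.8% v 7.5%, a gap of 1.3 points, and rejects in 4.0%. The level is never exceeded.

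**Step 6: no target lesion.** With k such patients in an arm and 50% DCR in the rest, ITT DCR = (0.5 × (62 − k) + s)/62, where s of the k have disease control. For k = 1 it runs from 49.2% (s = 0) to 50.8% (s = k). For k = 4 it runs from 46.8% to 53.2%. The shift is 0.8 to 3.2 points either way.

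**The case against.** The case for leaving the plan alone is substantial.

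- **The exception helps.** A reader might take the sentence on early progression and cancer death as the fault. It is the safeguard: it keeps the clearest early failures in the denominator. The exclusion comes from the evaluation requirement, and what is left out is narrow. Both arms are also to be scanned at discontinuation (Protocol Tables 1 and 2, section 11.12), so exclusions may be few.
- **Bias is not shown.** A reader might infer that the plan favours TAS-114/S-1 or inflates false positives. The documents do not support this. Excess error in scenario A appears only at splits of 3:1 or more, and nothing in the documents points to one. A single table can be made to cross 0.05: responders 10/62 v 4/62 give p = 0.154 on ITT and p = 0.044 if all 12 exclusions fall in the first arm. That is a constructed extreme.
- **The remedy has the mirror weakness.** In scenario B, TR evaluable holds its level and the ITT failure rule does not. This stands, and is why both results should be shown.
- **The second name looks inherited.** The sentence follows Protocol 14.1.2.2.2, and the same phrase follows the explicit ITT statement for PFS in SAP 7.5.1. In each place the opening sentence names the set. This makes an actual switch of denominator less likely, but the text still needs correcting.
- **The change is disclosed.** That SAP section 8 omits the change of population might suggest concealment, but SAP section 5 announces it. Where it is recorded is a matter of layout.
- **Part is already reported.** SAP 7.2 tabulates exclusions, and 7.5.2.2 has a row for unevaluable patients. That row does not bring back patients already outside the set.

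The endpoint definition does not settle the matter either. Requiring objective evidence of response fixes the numerator; it does not say who belongs in the denominator.

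**Conclusion.** The point holds as a minor one. ORR and DCR are compared in a set that depends partly on events after randomisation, and SAP 7.5.2.2 names that set in two ways that differ when read with the protocol. The randomised comparison kept for PFS and OS is not kept here.

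Neither direction nor size of bias can be taken from the documents. Under the assumptions above, balanced exclusions only raise the reported rates in scenario A (DCR 55.4% against 50.0% at 6 of 62 per arm). For DCR, 6 v 3 stays within 5% and 9 v 3 does not. For ORR the gap is at most 1.3 points in the cases tried.

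ITT is preferred because it preserves randomisation, matches PFS and OS, and fits the SAP's own ICH E9 rationale. The numbers do not show it to be better in every case. These are secondary endpoints with no stated alpha, and the synopsis calls their summaries descriptive. Parts of the relevant SAP sections are redacted and may hold a definition of the efficacy population or an ITT analysis. An ITT analysis there would not change the stated TR evaluable basis.

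**What to change.** In SAP 7.5.2.2, put in substance:

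> The main analysis of ORR and DCR uses the ITT population by assigned arm, with every randomised patient in the denominator. A patient without a qualifying best response by central review, including one with no post-baseline evaluation or no baseline scan, counts as a non-responder and as not having disease control. A patient with a baseline scan but only non-target disease stays in the denominator and is scored by protocol Table 14. The TR evaluable analysis is supportive and is shown beside the main one, with exclusions by arm and reason.

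Replace the reference to the efficacy population with the ITT population in both 7.5.1 and 7.5.2.2. If redacted text already holds an ITT analysis of ORR and DCR, make that the main one.

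**Cost.** SAP wording and a second denominator, before database lock; no new data and no change to sample size or the PFS analysis. Reported rates will usually be a little lower. If missing scans are unequal and unrelated to tumor control, the failure rule itself creates a gap (4.8 points at 9 v 3 in scenario B), so the supportive result must be read with it.

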##### **5.3 As-Treated (AT) Population**

The AT population is defined as all patients who received at least 1 dose of TAS-114 or S-1. All analyses using this population will be based on the treatment actually received. This population will be used for safety analyses.

CCI

## 6. SPECIFICATION OF ENDPOINTS AND VARIABLES

### 6.1 Demographic and Baseline Characteristics

Demographics, baseline characteristics, cancer history, medical history/active symptoms and prior cancer treatments will be collected at the baseline Day -28 visit; medical history/active symptoms will be confirmed (and updated as needed) at the baseline Day -7 visit and Cycle 1 day 1 visit:

- Demographic variables include age, sex, female reproductive status, race, ethnicity and geographic region. The age will be calculated as the integer part of (date of consent-date of birth)/365.25 for sites that collect date of birth. The age entered on the CRF will be used for sites that do not collect the date of birth.
- Baseline characteristics include height, weight, and ECOG performance status.
- Cancer history includes time from the initial diagnosis to first study drug dose, location of primary tumor, tumor grade, histology subtype, presence of metastases (yes vs. no), EGFR mutation (yes, no vs. unknown), ALK translocation (yes, no vs. unknown), ROS1 rearrangements (yes, no vs. unknown), and other gene abnormality (yes, no vs. unknown). Time from the initial diagnosis to first study drug dose (months) will be calculated as (first treatment dose date -date of original diagnosis) / 30.4375. Time from the metastatic diagnosis to first study drug dose (months) will be calculated will be calculated as (first treatment dose date- date of metastatic diagnosis) / 30.4375. If the day of the initial or metastatic diagnosis is missing, then the missing day will be imputed by the first day of the month for calculation purposes. If the day and month of the initial or metastatic diagnosis are both missing, then the missing day and month will be imputed by January 1st.
- Medical history and active symptoms include diagnosis or symptoms entered on the Medical History and Active Symptoms form. Verbatim descriptions of diagnosis or symptoms will be coded using the Medical Dictionary for Regulatory Activities (MedDRA version 19.0).
- Prior cancer treatments include medication/surgery entered on the Prior Radiotherapy form, the Prior Surgery form, the Prior Systemic Drug Therapies for Cancer form).
- Prior medication on Concomitant Medications and Therapies form. Prior medication is defined as any medication with start date on or before the first day of study drug (TAS-114 or S-1), or checked to be prior to first study drug administration date, or medication with start date missing.

Verbatim descriptions of prior medications will be mapped to the World Health Organization (WHO) Drug Dictionary Enhanced (WHO-DDE) and Herbal Dictionary (WHO-HD) (version Q1 2016).

### 6.2 Efficacy

#### 6.2.1 Primary Efficacy Variables

Progression-free survival (PFS) is defined as the time (in months) from the day of randomization to the start of radiologic disease progression or death (any cause), whichever occurs first: (earlier of: date of first radiologic PD or date of death [all cause] – date of randomization +1)/30.4375.

Progressive disease (PD) events assessed by the central independent review (blinded radiological review) will be used for primary efficacy analysis. Central tumor imaging assessments will be performed using RECIST guidelines (Version 1.1, 2009).

Patients who do not have disease progression or have not died will be censored at the last known time that the patient was progression free (e.g. date of last evaluable tumor assessment) before receiving any new anti-cancer treatment. Patients without disease assessment post-baseline will be censored at the time of the randomization.

Refer to **Table 3** for censoring rules for progression-free survival.

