14.1.2.1. Primary Efficacy Analysis

14.1.2.1.1. Progression Free Survival

PFS is defined as the time from the day of randomization to the start of disease progression or death (any cause), whichever occurs first, based on the blinded radiological review assessment of response. Patients who do not have disease progression or have not died will be censored at the last known time that the patient was progression free.

PFS in the efficacy population will be compared between the 2 treatment groups using the stratified log-rank test with significance level of one-sided 5%. PD events assessed by the central independent review will be used for primary efficacy analysis. The estimate of the hazard ratio and corresponding 90% and 95% confidence interval (CI) will be provided using a Cox proportional hazards (CPH) model including treatment and the 2 stratifications factors in the model. The survival curves will be estimated using the Kaplan-Meier method. The primary analysis for PFS will be conducted after 60 events have been observed based on independent assessment or after all patients have been followed for at least 3 months, whichever is later.

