**Table 3 – Censoring Rules for Progression-Free Survival**

Situation	End Date	Censored
Documented radiological PD	Date of the first tumor assessment that determined PD	No
Death during the study before PD	Date of death	No
Treatment discontinuation for other than radiologic PD or death with no post-baseline tumor assessments	Date of randomization	Yes
Treatment discontinuation for other than radiologic PD or death with post-baseline tumor assessments	Date of last adequate tumor assessment prior to initiation of non-study anti-cancer treatment	Yes
Patients still followed without radiologic PD as of cut-off date	Date of last adequate tumor assessment prior to cut-off date	Yes
Non-study anti-cancer treatment initiated before radiologic PD	Date of last adequate tumor assessment prior to initiation of non-study anti-cancer treatment	Yes
Death or radiologic PD after a missed (or not available/not evaluable) tumor assessment	
Date of last adequate tumor assessment prior to missed tumor assessment
 
A response assessment is considered “missed” if more than 13 weeks (91 days) has elapsed since the last image-based response assessment. If a patient develops progressive disease or dies after this interval, the tumor response assessment will be excluded from the analysis and censored at the last evaluable assessment. However, if a response assigned as CR, PR, or SD is obtained after more than 13 weeks, then the tumor response assessment will not be excluded from the analysis as long as no other censoring events have occurred.
 
Note: If patient dies within the 13 weeks from the last non-PD tumor assessment, death will be counted as a PFS event
	Yes

	unless the non-study anti-cancer treatment is initiated.	
Only non-evaluable (NE) tumor assessments after CR, PR, or SD	Date of last adequate tumor assessment prior to NE tumor assessments	Yes
No baseline tumor assessment	Date of randomization	Yes

General Considerations:
 
Tumor response assessment dates will be assigned based on the date the image was performed, not the date the image was assessed.
		

**Note:** Tumor response assessments will be considered “adequate” for analysis if they are assigned as CR, PR, SD, or PD and are not censored (e.g., obtained within 13 weeks since the last assessment and prior to initiation of non-study anti-cancer treatment: systemic anti-cancer therapy, radiotherapy or cancer surgery).

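### SAP Table 3 gives two outcomes for a death after unscanned discontinuation, no clock start without a post-baseline scan, and a 91-day limit that censors PD at the next scheduled scan after one missed 9-week scan

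*SAP*

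**What the plan says.** Protocol 14.1.2.1.1 makes any death an event: "PFS is defined as the time from the day of randomization to the start of disease progression or death (any cause), whichever occurs first". Its only censoring rule begins "Patients who do not have disease progression or have not died will be censored at the last known time". It has no rule for missed scans.

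SAP 6.2.1 keeps that definition and then adds "Patients without disease assessment post-baseline will be censored at the time of the randomization". Table 3 (PFS censoring rules) contains these rows:

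- "Death during the study before PD": an event on the date of death.
- "Treatment discontinuation for other than radiologic PD or death with no post-baseline tumor assessments": censored at the date of randomization.
- Missed assessment: a scan counts as missed "if more than 13 weeks (91 days) has elapsed since the last image-based response assessment". A later PD or death is censored at the last evaluable assessment, but "if a response assigned as CR, PR, or SD is obtained after more than 13 weeks", that scan is kept. A note adds: "If patient dies within the 13 weeks from the last non-PD tumor assessment, death will be counted as a PFS event", unless non-study anticancer treatment has begun.

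Table 4 applies the same 91-day limit to duration of response.

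On timing, protocol 11.12 and footnote 8 of both study schedules set scans every 6 weeks with a window of 7 days either way. They allow a change to every 9 weeks after Cycle 6. The baseline image may be up to 28 days before Day 1.

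**The concern.** There are three gaps in the rules for the primary endpoint.

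(a) Two Table 3 rows apply to the same patient: one who stops treatment for a reason other than radiologic PD, has no post-baseline scan, and dies before any new anticancer therapy. Such patients can occur. Protocol 11.12 requires treatment to stop at clinical progression without radiologic evidence, and 10.4.3 follows survival even after consent for other procedures is withdrawn.

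(b) The 13-week clock runs from an assessment that this patient may not have. The start could be the baseline image or randomization; the SAP does not say.

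(c) One fixed limit serves two scan intervals, and it fits only the shorter one.

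At stake is whether a few true deaths and progressions count in the primary test. Two programmers could each follow the SAP faithfully and reach different event counts.

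**Working it through.** **The plan's own figures.** Inputs from SAP 3.5: hazard ratio 0.524, one-sided alpha 0.05, power 80%, 1:1 allocation. Schoenfeld: 4 × (1.645 + 0.842)² / (ln 0.524)² = 59.2, so 60 events; power at 60 is 0.805. Investigator events: 60 / 0.85 = 70.6, so 71. Patients: 71 / 0.65 / 0.90 = 121.4, so 122 against the stated 124. The event target is reproduced and not in dispute.

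**(a) Rows side by side.**

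- Death while still on treatment, never scanned: the discontinuation row does not apply, so the death row makes it an event. Only the general no-scan sentence pulls the other way.
- Discontinued, scanned at least once after baseline, then died: the note makes a death within 13 weeks of the last non-PD scan an event if no new therapy has started.
- Discontinued, never scanned, then died: the death row says event; the no-scan row and the 6.2.1 sentence say censor at randomization. The note gives no answer unless a baseline image counts as a non-PD assessment, which is not stated.

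Only the third case is in true conflict between rows.

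**(b) Clock start.** Suppose the week-6 scan is missed and PD is found on day 84, taking randomization as Day 1. From randomization, 84 is within 91, so it is an event. From a baseline image taken d days before Day 1, the gap is 84 + d, which exceeds 91 when d is 8 to 28. If d is uniform on 1 to 28, that is 21/28 = 75% of patients.

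**(c) Gap to the next scheduled scan after one missed scan** (two intervals, with windows of 7 days at each end):

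- 6 + 6 weeks: 84 days, range 70 to 98. Nominally inside 91.
- 6 + 9 weeks, across the transition: 105 days, range 91 to 119.
- 9 + 9 weeks: 126 days, range 112 to 140. Always beyond 91.
- 9 weeks on time: 63 days, range 49 to 77. Unaffected.

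Only patients event-free at week 18 (4.14 months) can be on 9-week scans. Under the design medians this is 62 × 2^(−4.14/4.2) + 62 × 2^(−4.14/2.2) = 31.3 + 16.8 = 48 of 124.

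**Size.** Simulation, 2000 trials in each of 12 settings: 62 per arm, exponential PFS with the design medians, uniform 10-month accrual, 10% lost to tumor follow-up, 15% of PDs not confirmed centrally, baseline image uniform over 1 to 28 days, cut-off at the later of 60 central events or 3 months after the last patient, unstratified log-rank. The documents do not give rates for the following, which are assumed: 5% or 10% of scans missed at random, 10% or 20% of events being deaths, and 0, 50 or 100% switching to 9-week scans. With full switching there are 71 to 73 events at cut-off. Each issue was switched alone.

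- (a) Never-scanned deaths total 3.2 to 6.6, most of them plainly events. The conflicting share is unknown. At 10% to 50% it is 3.2 × 0.10 = 0.3 to 6.6 × 0.50 = 3.3 patients. The one-sided 5% result differs in 0.8–1.5% of trials at a 10% share and 2.3–4.3% at 50%.
- (b) Baseline-image against randomization clock: 1.3–1.4 events at 5% missed and 2.5–2.8 at 10%. The result differs in 1.4–1.6% and 2.1–2.7% of trials.
- (c) Events dropped by the 91-day limit if all switch, minus those dropped if none do: 1.58 − 0.51 = 1.07 and 1.44 − 0.46 = 0.98 at 5% missed; 3.06 − 1.21 = 1.85 and 2.78 − 1.10 = 1.68 at 10%. Against a limit that follows the scan interval, the result differs in 0.6–0.8% and 1.2–1.5% of trials.

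The mean shift in log HR is at most 0.013, from (c). The standard error at 72 events is about 2/√72 = 0.24, so the shift is about 5% of one standard error. As a crude check on the target, 71 − (3.3 + 2.8 + 3.1) = 61.8 events remain even if the upper figures are added together, using the gross drop of 3.1 for (c).

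**The case against.** The intent behind (a) is fairly clear. The sentence just before the no-scan sentence confines censoring to patients without progression or death, and the definition and the death row both count deaths. Scans are also due at or after discontinuation, so few patients should go unscanned. This shows how the conflict should be resolved, but the no-scan sentence and the discontinuation row still say otherwise, and nothing ranks them.

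On (b), a baseline scan carries no response category, so it is the weaker starting point. If the clock starts at randomization, or does not start at all, the day-84 PD is an event. That stands: the 1.3 to 2.8 events arise only under the weaker reading, and the point is a missing definition.

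On (c), a reader might infer that one missed 9-week scan always breaches the limit. It does so only for PD at the next scheduled scan. A death, an unscheduled scan or a discontinuation scan by day 91 is inside the limit, and the 9-week schedule is optional and late. A reader might also call it arbitrary to keep a late non-PD scan and drop a late PD. It is not: the former shows no progression in the gap, while the latter has an uncertain date.

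Nor can one conclude that the plan lacks a sensitivity analysis. Parts of SAP 7.5.1 are redacted, and the analysis code in Appendix 2 is not visible.

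**Conclusion.** The conflict in (a), the undefined clock in (b) and the mismatch in (c) can all be read directly in the SAP. They are minor. Under the assumed rates each moves about 1 to 3 of about 72 events, and the 60-event target is not at risk. The number of conflicting deaths is not given by the documents and was set by assumption.

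A reader might infer that the primary test is biased or underpowered; the documents do not support that. The simulated drops across a 9-week interval at 10% missed are nearly even by arm (1.35–1.48 on TAS-114/S-1, 1.19–1.31 on S-1). Informative missingness was not simulated. It cannot be excluded in an open-label trial whose two schedule tables, in footnote 8, describe off-treatment scanning differently; those passages should be reconciled.

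The absence of the missed-scan rule from SAP section 8 is a housekeeping matter, since protocol section 14 leaves technical detail to the SAP.

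**What to change.** In SAP 6.2.1 and Table 3:

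1. State that death before PD and before new anticancer therapy is an event and takes precedence over the discontinuation/no-scan row and the no-scan sentence, subject to the 13-week limit in item 2.
2. State that with no post-baseline scan the 13-week clock runs from randomization. Censor at randomization a never-scanned patient who is alive, who starts new anticancer therapy before PD or death, or whose PD or death falls beyond the limit. Every case then has an end date.
3. Keep 91 days for the primary analysis. Unless the redacted 7.5.1 text already does so, add a sensitivity analysis that counts all PDs and deaths regardless of missed scans. An alternative is to define a missed scan by the interval in force: two intervals plus windows, that is 98, 119 or 140 days.
4. Report by arm the PDs and deaths censored under each rule.

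Listing the missed-scan rule in section 8 is optional. The cost is a few sentences and a little programming before database lock, and slightly less certain dates for a few late progressions in the sensitivity analysis. The interval-based alternative also requires identifying each patient's scan schedule, which the count-all version avoids.
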